5.1 Primary endpoint

[REDACTED]

5.2 Secondary efficacy endpoints

[REDACTED]

5.3 Exploratory efficacy endpoints

[REDACTED]

[REDACTED]

5.4 Safety endpoints

[REDACTED]

5.5 Pharmacokinetic endpoints

[REDACTED]

5.6 Quality of life

[Redacted text block]

- [Redacted list item]
- [Redacted list item]
- [Redacted list item]

[Redacted text block]

6 TRIAL TREATMENTS

6.1 Allocation to Treatment

Patients will be assigned identification numbers as described in section 4.3.

6.2 Drug Supplies

Doxorubicin Transdrug (DT) will be supplied by the Sponsor as an investigational medicinal product (IMP). The IMP will be packaged, labeled and released according to current good manufacturing practice (GMP) guidelines, GCP guidelines and national legal requirements (as applicable).

In the control group, patients will receive the usual standard of care as decided by the investigator. The standard of care treatment will be handled, used and stored according to local's practice.

DT Formulation and Packaging

██████████ s ██████████ for suspension for injection that is to be reconstituted with 25 mL of glucose 2,5% for injection and filtered. See Appendix VII for details on study drug preparation procedures:

Name	Doxorubicin Transdrug™ 10 mg
INN	Doxorubicin
Excipients	██ ██ ██
Pharmaceutical Form	powder for suspension for injection
Route of Administration	Intravenous
Method of Administration	Slow IV infusion of 6 hours
Dosage Strength and Form	10 mg/vial
Name of Manufacturing Laboratory	██
Packaging	██
Distribution	██ ██
Storage	5°C ± 3°C

DT Dispensing

The investigational products will be sent from ██████████ to the pharmacy of each investigational centre, which will ensure storage, dispensation and the reconstitution for each Cycle.

6.3 DT Administration

In DT groups, based on DSMB recommendation after their careful review of the safety profile reported in the first 75 patients, a shorter period of hospitalization could be recommended since

version 5.0, June 10th, 2014 as compared to the previous protocol version. The premedication will be unchanged as compared to the previous protocol version and administered to the patient according to each centre's usual practice. On D0, one day before each DT administration, patient will be hospitalized or will have an outpatient visit to check eligibility criteria for continuing treatment and to ensure that the premedication is taken. Patient will receive DT infusion on D1 and will be hospitalized until D2. Patient could be discharged on D2 or on D3 in the absence of toxicity. Hospitalization until D3 is optional.

Hospitalization or outpatient visit on D0 and prolonged hospitalization until D3 will be adapted according to hospital practice and/or patient preference.

Day 0 defined as one day before the treatment with DT

- Premedication with methylprednisolone 32 mg p.o. (or equivalent) and cetirizine 20 mg p.o.(or equivalent);

Day 1 : Day of therapy with DT

- H-1: premedication with methylprednisolone 32 mg p.o. (or equivalent) and cetirizine 20 mg p.o.(or equivalent);
- Fasting is not needed;
- **H0:** 20 mg/m² or 30 mg/m² of DT will be prepared and infused over 6 hours through intravenous route (Appendix VII).
- Patient will have a continuous SaO₂ monitoring during infusion and the 24 hours after the infusion start.

Any modification in the infusion rate must be recorded in the e-CRF (see section 7.6: safety measures).

Day 2 : The day after the DT therapy:

- Premedication with methylprednisolone 32 mg p.o. (or equivalent) and cetirizine 20 mg p.o.(or equivalent);

D0 = D28

Each Cycle will be repeated every 28 days up to progression or toxicity.

6.4 Best Standard of Care administration

The patient in BSC group will be treated and monitored according to the centre's usual practice. Patients will receive BSC as judged by their treating physician. Those therapies considered acceptable include, but are not limited to, anticancer therapy and/or supportive care (e.g. antibiotics, analgesics, antiemetics, ascitis drainage, blood transfusions, and/or nutritional support (enteral or parenteral)). If it is unclear whether a therapy would be regarded as BSC, Onxeo (formerly known as BioAlliance Pharma) should be consulted.

6.5 Compliance

Patients in the DT arm need to be hospitalised at the investigational site to receive the study therapy. Patients in the control arm may not be hospitalized if the local practice doesn't require hospitalisation for the study therapy administration. However, per protocol, they should comply with the planned visits on days 1 and 14 of each cycle.

For the DT groups : the drug accountability will be assessed by recording the dispensation of treatment. The investigator and/or the hospital pharmacist must keep an up-to-date drug dispensing log containing the following information:

- Identification of the patient to whom the medication was dispensed
- Dates of the study drug administered to the patient
- The total dose administered to the patient

The investigator or the hospital pharmacist must only use DT for patients participating in the study.

For BSC group: The patient will be treated according to the centre's usual practice and no drug accountability is required. Any treatment administered to the patient (usual supportive care and/or anticancer treatment) will be recorded in the e-CRF.

6.6 Dose adjustment, dose delay and infusion duration

6.6.1 Dose Adjustment: DT Arms

Dose adjustment will be based upon haematologic and non haematologic toxicities observed after the previous dose administration.

All dose reductions for patients randomised to receive either treatment A (DT 20 mg/m²) or B (DT 30 mg/m²) will be calculated based upon the following dose level reduction guidelines.

Dose level reduction guidelines:

Arm A (DT 20 mg/m²)

Initial Dose Level	20 mg/m ²
Dose Level -1	15 mg/m ²

Arm B (DT 30 mg/m²)

Initial Dose Level	30 mg/m ²
Dose Level -1	20 mg/m ²
Dose Level -2	15 mg/m ²

Haematologic criteria for dose modifications:

- In case of grade 3 (500 – 1000/mm³) or grade 4 (< 500/mm³) neutropenia whatever the duration of neutropenia and/or in case of grade 3 (25 000 – 50 000/mm³) or grade 4 (< 25 000/mm³) thrombocytopenia, DT will be interrupted until resolution to a grade ≤ 2.

A new cycle of DT could be administered only if neutrophil count \geq grade 2 ($\geq 1000 /\text{mm}^3$) and platelets count \geq grade 2 ($\geq 50,000 /\text{mm}^3$).

- In case of grade 4 neutropenia ($< 500/\text{mm}^3$) lasting > 7 days, grade 4 febrile neutropenia of any duration and grade 4 thrombocytopenia ($< 25,000/\text{mm}^3$), the dose to be administered will be the minus 1 dose level (refer to the table below).
- If the haematologic toxicity has not returned to grade ≤ 2 , the cycle will be delayed to a maximum of 4 weeks. In case of persistent (more than 4 weeks) haematologic toxicity $> \text{grade } 2$, the treatment should be definitively stopped (i.e. patient will not receive any additional DT infusion).
- Any patient who requires a dose reduction will be treated with a reduced dose for any subsequent doses.
- Arm A patients requiring dose reductions below dose level -1 must discontinue. Arm B patients requiring dose reduction below dose level -2 must discontinue.

DT dose level decrease in case of haematologic toxicity recovering to grade ≤ 2

Drug Related Toxicity	DT dose level
Grade 4 neutropenia ($< 500/\text{mm}^3$) lasting > 7 days	Decrease 1 level
Grade 4 Febrile neutropenia of any duration	Decrease 1 level
Grade 4 thrombocytopenia ($< 25,000/\text{mm}^3$)	Decrease 1 level

Non haematologic criteria for dose modifications:

- In case of ARDS, the patient will be definitively stopped from the DT therapy (i.e. patient will not receive any additional DT infusion).
- In case of life-threatening serious and non haematologic AE related to DT, the treatment will be definitively stopped (i.e. patient will not receive any additional DT infusion).
- In case of grade 3 or grade 4 non haematologic toxicity related to DT (e.g. nausea/vomiting, stomatitis, asthenia... despite adequate/maximal medical intervention and/or prophylaxis), a resolution to a grade ≤ 2 has to be observed to initiate a new cycle. The dose to be administered will be the minus 1 dose level. If the non haematologic toxicity has not returned to grade ≤ 2 , the cycle will be delayed to a maximum of 4 weeks. In case of persistent (more than 4 weeks) non haematologic toxicity $> \text{Grade } 2$, the treatment should be definitively stopped (i.e. patient will not receive any additional DT infusion).

Any patient who requires a dose reduction will be treated with a reduced dose for any subsequent doses.

Arm A patients requiring dose reductions below dose level -1 must discontinue. Arm B patients requiring dose reduction below dose level -2 must discontinue.

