7.6.3 Liver toxicity

Cirrhosis may decompensate and liver function may deteriorate in cirrhotic patients. Clinical signs and symptoms and liver function tests will be closely monitored throughout the study, before each study treatment administration, then every day for 3 days, at days 14 and 28 during each cycle.

In case of aggravation of liver function tests, the investigator may prolong the hospitalisation, take all appropriate measures and administer symptomatic treatments as required. **If hospitalisation is prolonged (> Day 3), investigator should inform Onxeo (formerly known as BioAlliance Pharma), fill in and fax a SAE form.**

Further DT infusions should be performed only if liver function tests returned to baseline values with a Child-Pugh score from A5 to B7 included (if cirrhosis) and serum bilirubin $< 35 \mu\text{M/L}$ (or 2.0 mg/dL) (see section 6.6).

Infusion could be delayed by up to 4 weeks. Dose reduction is authorized as described in section 6.6.1.

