7.6.4 Cardiac toxicity

Cardiac toxicity has been reported with doxorubicin. Congestive heart failure (CHF) is among the most serious toxicities of doxorubicin, increases with the cumulative dose of doxorubicin, and is estimated to be 5 % at a cumulative dose of 400 mg/m^2 , 16 % at 500 mg/m^2 and 26 % at 550 mg/m^2 . To date, no cardiac events have been reported in patients suffering from HCC and treated with DT.

According to the potential cardiac risk, LVEF will be monitored every other month and ECG every month before each infusion.

In case of ECG modifications or any symptoms associated to a decreased LVEF and/or LVEF below the lower limit of normal values, additional DT infusions will not be authorized until a cardiologist is consulted for aetiologic work-up. The investigator will decide whether further DT infusions should be performed or definitively stopped, taking into account the benefit/risk ratio.

Infusion could be delayed by up to 4 weeks. In case of grade 3 or 4 related adverse events, dose reduction is authorized as described in section 6.6.1.

The maximum authorized cumulative dose of doxorubicin is 550 mg/m² (or its equivalent for other anthracyclins).

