7.6.5 Any other adverse events

In case of any other grade 3-4 toxicity at the time of next infusion, the infusion should be delayed by up to 4 weeks until AE decreases to grade ≤ 2 . In case of persisting grade 3-4 AE, the study treatment will be definitively stopped.

In case of life-threatening serious AE related to DT, the treatment will be stopped and the patient will not be re-administered DT.

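### The visible re-treatment checklists leave out exclusion criterion 8's 4-week digestive-bleeding bar; the synopsis also states the life-threatening stop more narrowly than 6.6.1 and 7.6.5

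*Combined protocol and SAP*

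**What the plan says.** **Bleeding.** Exclusion criterion 8, in both the synopsis and section 4.2, concerns patients at risk of variceal bleeding, who may enter after preventive treatment. It ends with a sentence about giving the drug: DT is withheld if digestive bleeding occurred in the preceding 4 weeks. Section 6.6.2 and the synopsis then list what must be met before each new infusion. The bleeding item there asks for no clinical sign of an upper gastrointestinal bleed. It has no time window and does not mention lower bleeding. The same list requires haemoglobin of at least 10 g/dL. Under 6.6.2 an unmet item delays the infusion for at most 4 weeks, after which the patient leaves study treatment. Section 6.3 sets a 28-day cycle with DT on Day 1.

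**Life-threatening reactions.** The non-haematological part of 6.6.1 says "In case of life-threatening serious and non haematologic AE related to DT, the treatment will be definitively stopped" and explains that no further infusion follows. The next bullet opens "In case of grade 3 or grade 4 non haematologic toxicity related to DT", requires recovery to grade 2 or lower before a new cycle, and then says "The dose to be administered will be the minus 1 dose level". Section 7.6.5 repeats the stop: "In case of life-threatening serious AE related to DT, the treatment will be stopped and the patient will not be re-administered DT". The synopsis gives a permanent stop only for ARDS and related life-threatening respiratory events, and a delay of up to 4 weeks for grade 3-4 events.

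**The concern.** The 6.6.2 list is what a site works from when deciding whether to infuse. If criterion 8's bar is meant to hold throughout treatment, the list is weaker than the rule in two ways: it drops the 4-week window, and it narrows digestive bleeding to upper gastrointestinal bleeding. A site that follows the list faithfully could re-dose a patient with liver disease sooner after a bleed than the protocol states elsewhere. Such bleeds are foreseeable, because patients with treated high-risk varices may enter.

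The second, smaller issue is that a site working from the synopsis sees a narrower permanent stop than the body sets. In 6.6.1 the bullet on restarting at a lower dose does not say that it leaves life-threatening events to the bullet before it.

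What is at stake is the safety of individual patients and consistent dosing across about 100 centres.

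**Working it through.** The plan gives no figure to reproduce here. The check is a comparison of rules plus calendar arithmetic.

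**Inputs**
- Section 6.3: Day 0 of the next cycle is Day 28 of the current one, and DT is given on Day 1, so the next infusion is due on Day 29.
- Criterion 8: 4 weeks, that is 28 days, after digestive bleeding.
- Section 6.6.2: maximum delay of 4 weeks, so the last permitted day is 29 + 28 = Day 57.

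**Which bleeds fall inside the window.** For a bleed on Day b, criterion 8 read as a dosing rule permits DT from Day b + 28. This is later than Day 29 whenever b is 2 or more. Within the cycle that covers Days 2 to 28, which is 27 of 28 days. This describes the calendar only. The documents give no bleeding rate, so it is not a frequency of events.

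**Delay needed.** Delay = (b + 28) − 29 = b − 1 days.

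| Bleed on Day b | DT permitted from Day b + 28 | Delay, b − 1 days |
|---|---|---|
| 2 | 30 | 1 |
| 14 | 42 | 13 |
| 28 | 56 | 27 |

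All three fall on or before Day 57. If the 28th day is counted as still barred, each delay grows by one day. The longest is then 28 days, still at the limit. A further bleed after Day 29, while an infusion is already on hold, would not fit: a bleed on Day 30 gives 30 + 28 = Day 58.

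**The two bleeding rules side by side on Day 29**
- Upper gastrointestinal bleed on Day 14, resolved, haemoglobin at least 10 g/dL, other items met: the visible list allows DT; criterion 8 bars it until Day 42.
- Lower digestive bleed on Day 14, same conditions: the list's bleeding item does not apply; criterion 8 bars DT until Day 42.
- Upper gastrointestinal bleed still clinically evident: both bar DT.

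**The life-threatening rules side by side.** Take a DT-related, non-respiratory, non-haematological grade 4 event that put the patient at risk of death (the 8.3 definition) and then recovered to grade 2 or lower.
- 6.6.1, stop bullet: no further DT.
- 7.6.5: no further DT, with no limit by organ.
- 6.6.1, next bullet: its trigger is met as worded, with no exception stated.
- Synopsis: the specific stop does not apply, because the event is not respiratory; the grade 3-4 delay does.

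The overlap need not cover every grade 4 event. Section 8.4 equates grade 4 with life-threatening only for events that the CTC does not list.

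**The case against.** **On bleeding.** If criterion 8 is a dosing rule, it already bars the infusion, and it appears in two places; the checklist adds a condition and does not cancel it. If criterion 8 applies only at entry, there is no conflict. This is fair, and the point depends on which reading the sponsor meant. It does not remove the need for a change: the sentence is worded around giving DT, and a list of conditions for every infusion should carry a standing bar or leave no doubt that there is none. Section 6.3 also places a check of eligibility to continue on Day 0. The Day 0 and Day 1 procedures (7.2.1.1 and 7.2.1.2) are redacted, and the content of 7.2.2 and 7.2.3 is not shown. Any of these may repeat the 4-week condition, so the gap is established only for the two visible lists.

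**On life-threatening events.** A reader might infer that the protocol allows re-dosing after such a reaction, or that its rules contradict each other. The documents do not support that. The 6.6.1 stop is absolute, while the next bullet only sets conditions for a new cycle, and after a permanent stop there is none. Its examples (nausea, stomatitis, asthenia) show its ordinary target. Section 7.6.1 has its own respiratory stop and needs no added cross-reference. Section 7.6.3 says "Infusion could be delayed by up to 4 weeks. Dose reduction is authorized as described in section 6.6.1" and 7.6.4 says "In case of grade 3 or 4 related adverse events, dose reduction is authorized as described in section 6.6.1"; both send the reader to the section that contains the stop.

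A reader might also take this sentence in 7.6.4 as an override: "The investigator will decide whether further DT infusions should be performed or definitively stopped, taking into account the benefit/risk ratio". It follows ECG changes or a reduced LVEF and a cardiology consultation, and does not address life-threatening events. The heart-failure estimates in that section are for doxorubicin by cumulative dose and measure nothing about an unclear stop rule.

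**Safeguards.** The investigator or sponsor may take a patient off drug at any time (4.4). Serious events reach the sponsor (8.7.2) and the DSMB (7.4) within 24 hours or by the next working day. These reduce the risk but rely on case-by-case judgement.

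**Conclusion.** The bleeding inconsistency holds on the visible text and is the main point. For 27 of the 28 cycle days, a resolved digestive bleed passes the list's bleeding item while falling inside criterion 8's window at the next due infusion. This assumes that criterion 8 is a dosing rule, that the remaining checklist items are met, and that the redacted procedures do not restore the window. The number of patients affected cannot be estimated from the documents.

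The life-threatening part is a minor clarification. Stopping first is the natural reading, and 6.6.1 and 7.6.5 both state the stop. What remains is a missing exception in one bullet and a synopsis narrower than the body. The synopsis also ends treatment for unacceptable toxicity, but the visible text does not define that term.

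Overall this is a cheap patient-safety improvement. It does not touch the sample size, power or type I error. A reader might look for a consequence for the overall survival test or the 9.6 dose selection; none is shown.

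**What to change.** 1. In 6.6.2 and the synopsis list, replace the bleeding item with: *no clinical evidence of digestive bleeding, and no digestive bleeding in the previous 4 weeks*. If the sponsor meant criterion 8 to apply only before the first infusion, say so in criterion 8 instead.
2. In the synopsis, widen the permanent stop to any DT-related life-threatening non-haematological serious event, to match 6.6.1 and 7.6.5.
3. In the grade 3-4 bullet of 6.6.1, add: *other than life-threatening events*.

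The cost is a wording amendment and a letter to sites, with no new data or procedures. The downside is some delayed infusions: b − 1 days for a bleed on Day b of the cycle, within the present 4-week maximum. A patient who bleeds again after Day 29, during a hold, would pass that maximum and leave study treatment under 6.6.2; the sponsor should confirm that this is intended.

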6.6.2 Dose Delay: DT arms

To initiate a new DT infusion, the patient needs to meet the following continuing treatment criteria:

- Adequate liver function:
 - Child-Pugh score from A5 to B7 included (if cirrhosis)
 - Serum bilirubin < 35 µM/L (or 2.0 mg/dL)
- Adequate respiratory function defined as SaO₂ ≥ 95%;
- Absence of ongoing infection
- Adequate haematologic tests :
 - Neutrophil count ≥ 1000 /mm³
 - Platelets count ≥ 50,000 /mm³
 - Haemoglobin ≥ 10 g/dL
- No clinical evidence of upper gastrointestinal bleeding
- No other limiting toxicity > grade 2

If one of these criteria is not met, the next infusion should be delayed for a maximum of four weeks. In case one of these criteria is not met after the 4 weeks delay, the patient will be withdrawn from the study treatment period and the end of therapy notification form will be completed.

6.6.3 DT Infusion duration

DT will be administered as a protracted i.v infusion during 6 consecutive hours. That infusion duration will be prolonged up to 12 consecutive hours if any of the condition described in section 7.6 occurs. In case of accidental infusion acceleration, i.e accidental infusion duration ≤ 2 hours, urgent safety precautions should be rapidly available at the patient bedside. Those measures include, but are not limited to, mechanical respirator and supplemental oxygen, i.v corticosteroids, i.v antibiotics if infection is suspected.

The maximum allowed cumulative dose of doxorubicin (or equivalent) is < or equal to 550 mg/m² (this takes into account prior anthracyclins cumulative dose and DT cumulative dose).

6.6.4 Best Standard of Care Arm

Throughout the study, dose adjustment or delay in the BSC arm will be based upon the specific standard of care and according to local practice.

6.7 Drug Storage and Drug Accountability

The investigational product (DT) will be stored in a secure limited access area at 5°C± 3°C. The pharmacist at the trial centre will be responsible for the correct storage, handling of the study products and for all the documentation on drug supplies.

A drug movement form of all investigational products dispensed during the study will be maintained.

All investigational materials (medication and packaging) unused in the study will be returned to [REDACTED] (or its designee) before, or at the termination of the study, together with an accountability form.

All DT administered units will be destroyed on site, according to routine hospital practice and current national guidelines/regulations.

6.8 Concomitant Medication(s)

As doxorubicin is metabolized by the liver and is a substrate of CYP3A4, CYP2D6 and P-gp, the concurrent use of inhibitors or inducers of CYP3A4, CYP2D6 and P-gp should be used with caution and based on the benefit/risk for the patient. A list of the most common CYP3A4, CYP2D6, P-gp inhibitors or inducers is provided in appendix XII. All treatments administered and date of administration must be recorded in the e-CRF. Use of any concomitant medication will be recorded in the e-CRF with the following information:

- reason for treatment;
- name of the drug, type of formulation, and unit strength;
- dose administered;
- duration of treatment.

